10.2 Study Population

All subjects who are consented into the clinical study will constitute the intention-to-treat (ITT) population for the purposes of adverse event reporting. Only subjects who completed per the protocol will be considered as the completed cases (CC) population and per protocol (PP).

10.3 Missing Data

All efforts will be put forth to ensure near complete follow-up, with focus on the assessment of the primary outcome and occurrence of adverse events. Regular reminders of subject follow-up due dates will be provided to participating centers to facilitate scheduling of follow-up visits.

11. Risk Benefit Statement

11.1 Benefits

It is possible but not guaranteed that advances to cochlear implant technology will improve performance or increase usability of devices for future recipients. This investigation will help to inform clinical guidance when fitting new cochlear implant patients. It cannot be promised that subjects will receive any medical benefits from being in this study.

11.2 Risks

With any cochlear implant mapping, there is a very small risk of unintentional over-stimulation. Subjects may experience sounds during mapping that are uncomfortably loud. Mitigation of this risk is similar to that used during clinical cochlear implant mapping wherein the sound processor is removed from the subjects' head and/or the stimulation to the sound processor is ceased in Custom

Sound. This is a modified clinical treatment plan and therefore the possibility of patient dissatisfaction and reduced performance.

12. Good Clinical Practices Statement

The study obligations for the Investigator(s) are outlined in guidelines for Good Clinical Practice (GCP), 21 CFR Part 812 (Code of Federal Regulations Part 812 Investigational Device Exemptions), ISO14155:2011 (Clinical Investigation of Medical Devices for Human Subjects – Good Clinical Practice), and the Declaration of Helsinki.

12.1 Access to Study Documents and Study Monitoring

Investigator(s) will provide access to study documentation including source data and electronic medical records for the purposes of monitoring, audits, IRB review, and regulatory inspections. The Sponsor will perform on-site and remote monitoring visits as frequently as necessary to oversee conduct, data collection and record keeping by sites. The clinical investigation monitoring plan is a separate document describing all the activities performed during site qualification, initiation, monitoring, and close out and is available for review.

12.2 Quality Control and Assurance

Study sites may be subject to Quality audits at any point during the study. Regulatory agencies may conduct inspections during the course of the clinical investigation and after study completion.

12.3 Institutional Review Board

Each site will obtain approval from its designated IRB prior to commencing any study-related activities. A copy of the IRB approval will be kept in the Investigator file(s). Any additional requirements imposed by the IRB and/or regulatory authority shall be followed. The Investigator(s) will submit the appropriate documentation if any necessary extension or renewal of the IRB approval must be obtained.

12.4 Informed Consent Process

Prior to recruitment of any subjects into the study, written approval of the investigational plan including clinical protocol and informed consent form will be obtained from reviewing Institutional Review Board (IRB). An interview (as part of the informed consent process) will be conducted by the surgeon and/or delegated

staff to inform the subject about rationale for and the details, aims, objectives of the study, study expectations, evaluation schedule, and the risks and benefits of the trial treatment (and alternative treatments), and the extent of the patient's involvement. Written informed consent shall be obtained from each subject after this explanation. After reviewing the Informed Consent Form, the subject will be given the opportunity to review and ask questions about the Informed Consent Form and/or the study prior to signing the Informed Consent Form. The subject will be offered the opportunity to take the form home to discuss with family members should they choose to do so. If they sign the Informed Consent Form, the subject will then be given a copy of the signed Informed Consent Form to take home. The informed consent process is intended to be completed after standard of care surgery but may be completed pre-operatively if deemed appropriate by the Investigator.

The Investigator is responsible for ensuring that all patients give written informed consent prior to any study-related examination or activity. All patients shall sign and date the Informed Consent Form, and a copy of the Informed Consent Form shall be given to the patient. The Sponsor and the Investigator(s) shall avoid improper influence on or inducement of the subject, monitor, the Investigator(s) or other parties participating in or contributing to the clinical investigation.

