Study Overview	
The clinical investigation is evaluating a new clinical model in a group of newly implanted subjects who have already been consented to CI surgery.
 
This randomized multi-center study will investigate a new model (Group A) based on outcome evidence, a standardized programming and testing method that utilizes artificial intelligence and will be compared to a traditional clinical model (Group B).

Primary Objective	To evaluate the total amount of clinical time as defined by number and duration of visits in a new model (Group A) compared to a traditional clinical care schedule (Group B)
Secondary Objectives	
 1. To compare speech perception in quiet as measured on CNC words in the implanted ear. 2. To compare subject hearing outcome satisfaction on the SSQ-12 between the two models. 3. To compare device and accessory use of subjects as measured by a device use questionnaire and datalogging between the two models. 4. To compare clinician satisfaction between the models through a questionnaire. 5. To compare speech perception in noise as measured on AzBio +10 S/N in their everyday listening situation using

	the subjects preferred noise program and accessory if appropriate.
Primary Endpoint	Reduction in the overall number of minutes of cochlear implant appointments over the first 6 months post activation in the new model (Group A) compared to the traditional model (Group B).
Secondary Endpoints	
 1. Speech perception on CNC at 3 and 6 months post activation will be the same or better in the new model group compared to the traditional model. 2. Subjective hearing outcome satisfaction on the SSQ-12 at 6 months post activation will be the same or better in the new model group compared to the traditional model. 3. Device and accessory use will be the same or better at 6 months of device use with the new model compared to the traditional model as measured by a device use questionnaire and datalogging. 4. Clinician satisfaction will be the same or better with the new model when compared to the traditional model at the 6-month interval. 5. Speech perception on Az-Bio +10 S/N at 6 months post activation in the subjects everyday listening condition will be better than the pre-operative score.

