4.3.1 Inclusion Criteria

1. Patients who are receiving a commercially available Nucleus® electrode
2. 18 years and older
3. Postlingual onset of hearing loss (onset of hearing loss >2 years of age)
4. Individuals who qualify for cochlear implantation using the clinics current CI candidacy criteria
5. Individuals who have recently been implanted but not yet had their external device activated
6. Willingness to participate in a study and comply with all study requirements
7. Fluent in spoken English

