5.4 Pre-operative Procedure

5.4.1 Preoperative Candidacy Evaluation

5.4.2 Informed Consent

A preoperative interview (as part of the informed consent process) will be conducted by the surgeon and/or audiologist to inform the candidate about all aspects of implantation with a cochlear implant, study goals and requirements, as well as the evaluation schedule. The potential limitations and advantages of cochlear implantation shall also be explained.

After reviewing the Informed Consent Form, the candidate will be given the opportunity to review and ask questions about the Informed Consent Form and/or the study prior to signing the Informed Consent Form. The candidate will be offered the opportunity to take the form home to discuss with family members should they choose to do so. If they sign the Informed Consent Form, the candidate will then be given a copy of the signed Informed Consent Form to take home.

A candidate is not considered enrolled until a properly executed Informed Consent Form has been obtained along with the results of the preoperative candidacy evaluation. CNC, AzBio at + 10 SNR, SSQ-12 and COSI completed prior to consent within 90 days will be accepted as part of the pre-op candidacy evaluation.

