5.4.3 Candidacy Baseline Assessment

The clinic will administer their typical candidacy baseline assessment for patients receiving a cochlear implant as standard of care. In addition, they will administer the following, if not part of the standard battery:

- New Model (Group A) and Traditional Model (Group B)
 - CNC Words: Two lists at 60 dBA with an appropriately fit hearing aid in the unilateral condition (contralateral ear plugged)
 - AzBio Sentences in Noise at 60 dBA at +10 dB S0N0 presented in the sound field for the everyday listening condition.
 - Patient reported outcomes:
 - SSQ-12
 - COSI
 - Hearing History: Information collected from the subject regarding the type and duration of their hearing loss.
 - Demographics: Characteristics of the subject population to include race, ethnicity and gender etc.
 - Device History: Current and previous use of hearing aids
 - Medical History: current or past medical conditions or surgical history relevant to the conduct of the study
- Eligibility: confirmation subject meets inclusion and exclusion criteria
- Randomization: Upon randomization, Group A subjects will receive the following:
 - A take home packet (at the candidacy evaluation or post-surgery) prior to the switch-on to provide them with information they will review as part of the self- learning.
 - Written instructions for scheduling a support call with Cochlear Recipient Services for counselling on external equipment and cochlear implant system. Call will be scheduled 2 weeks following initial activation.

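### With consent taken after surgery by default, a subject whose aided CNC or AzBio +10 was not routine, or is too old, cannot have a valid pre-operative score, and nothing in the protocol prevents this

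*Protocol*

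**What the plan says.** Protocol section 12.4 sets the usual timing of consent: "The informed consent process is intended to be completed after standard of care surgery". The same sentence goes on: "but may be completed pre-operatively if deemed appropriate by the Investigator". The section also makes the investigator responsible for obtaining "written informed consent prior to any study-related examination or activity". Inclusion criterion 5 (section 4.3.1) describes the people to be recruited as "Individuals who have recently been implanted but not yet had their external device activated".

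Section 5.4.3 lists the baseline measures for both groups. Beyond each clinic's own candidacy testing it states: "In addition, they will administer the following, if not part of the standard battery". The list includes two CNC lists with a hearing aid in the unilateral condition, AzBio sentences at +10 dB in the everyday listening condition, SSQ-12 and COSI. Section 5.4.2 accepts these four measures if they were done before consent, within 90 days.

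On enrolment, section 5.4.2 says: "A candidate is not considered enrolled until a properly executed Informed Consent Form has been obtained along with the results of the preoperative candidacy evaluation". Section 5.1 instead counts everyone who signs the consent form as enrolled.

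Secondary endpoint 5 (section 1) requires that AzBio at 6 months "in the subjects everyday listening condition will be better than the pre-operative score". Sections 5.5.4 and 5.5.5 use pre-to-post CNC gains of 20 and 30 to direct Group A visits, and section 10.1 counts subjects reaching those gains in both groups.

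**The concern.** A test given only because the protocol asks for it is a study procedure, so it has to wait for consent. If consent comes after surgery, the pre-operative state of the ear to be implanted has gone, and a pre-operative aided score can no longer be measured. Section 5.4.3 itself foresees clinics whose usual work-up lacks one of these tests, and those are the clinics where the usual consent timing fails.

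At stake are the comparison in secondary endpoint 5, the milestone counts in section 10.1, and the Group A decision rule at 3 and 6 months, which cannot be applied as written without a pre-operative CNC score. Any gap would follow site practice rather than chance, in a trial of at most 5 sites. A site trying to avoid the gap might test before consent, which section 12.4 forbids.

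**Working it through.** The protocol gives no figure to reproduce here. The check sets the rules side by side and follows each possible order of events.

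**Rules used**
- Consent normally after surgery, earlier at the investigator's discretion (12.4).
- No study procedure before consent (12.4).
- CNC and AzBio +10 added before surgery if not routine (5.4.3).
- Earlier results accepted within 90 days before consent (5.4.2).
- Subject already implanted but not activated (4.3.1, criterion 5).

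**Cases**
1. *Consent before surgery.* Missing tests can be done after consent and before the operation. A baseline is obtainable. Read literally, however, criterion 5 is not yet met when such a person signs.
2. *Consent after surgery, both tests done routinely within 90 days before consent.* Section 5.4.2 accepts them. A baseline exists.
3. *Consent after surgery, CNC or AzBio not part of the clinic's routine.* The test could not be given before consent, and after surgery it is no longer pre-operative. No valid baseline can be obtained.
4. *Consent after surgery, tests routine but done more than 90 days before consent.* The score exists and is truly pre-operative, but section 5.4.2 does not accept it, and it cannot be repeated.

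**The window.** Let d be the number of days from surgery to consent. A test done t days before surgery is accepted only if t + d ≤ 90, that is, t ≤ 90 − d. Each day that consent is delayed after surgery shortens the acceptable pre-operative period by one day, although the delay does not change how well the score represents the pre-operative state. The protocol gives neither t nor d, so the frequency of case 4 is unknown.

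**Which measures are lost.** The argument applies to CNC and AzBio, which depend on the ear before surgery. SSQ-12 and COSI are questionnaires, and the same impossibility is not shown for them.

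**What happens to a subject in case 3 or 4**
- Under section 5.4.2 the person is not enrolled, because the pre-operative results are lacking. The effect is selection and slower recruitment.
- Under section 5.1 the person is enrolled on signing. The effect is a missing baseline.

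**What needs the baseline**
- *Needed:* secondary endpoint 5; the milestone counts in section 10.1; the Group A review at 3 and 6 months.
- *Not needed:* the primary endpoint (appointment minutes over 6 months) and secondary endpoints 1 to 4 as worded, which compare the groups after activation.

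The Group A review helps decide whether further testing is done at the visit, so a missing baseline could touch appointment minutes indirectly. The protocol gives no means of sizing that.

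**The case against.** A reader might infer that the consent, testing and timing rules contradict each other outright. The documents do not support that. Section 12.4 expressly permits consent before surgery, section 5.4.2 describes a pre-operative consent interview, and Tables 1 and 2 in section 7 place informed consent in the Pre-Op column. An investigator at a clinic without the tests can take consent early, run them, and let surgery follow. For routine tests inside the window, section 5.4.2 also covers consent after surgery. All the rules can be met together.

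A reader might also infer that a sizeable share of the 35 to 50 subjects will lack a baseline. Nothing supports any particular share: the clinics' test batteries and waiting times are not given, and under section 5.4.2 a person without the results would not be enrolled at all.

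Both points stand, and they narrow the concern to cases 3 and 4. They do not remove it. Early consent is discretionary, nothing ties it to an incomplete work-up, and criterion 5 points towards recruiting after surgery. The 90-day rule accepts existing results but does not authorise non-routine testing before consent. Section 5.4.2 settles the outcome only if section 5.1 is disregarded.

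**Conclusion.** The concern holds in a limited form. For subjects consented after surgery whose CNC or AzBio +10 was not routine, or was done more than 90 days before consent, the protocol's own rules leave no valid pre-operative score. Secondary endpoint 5 and the pre-post CNC milestones then lack their baseline, and the protocol gives two answers on whether the person is enrolled.

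The number affected is not stated and could lie anywhere from none to all of the 35 to 50 subjects. The conclusion assumes that a test outside a clinic's routine counts as a study procedure, and that the 90 days run back from consent, as section 5.4.2 is worded. The primary endpoint and the between-group secondary endpoints do not require the baseline. The point still deserves an amendment, because no later analysis can recover a pre-operative score that was never collected.

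**What to change.** In sections 12.4 and 5.4.2:
- Require consent before surgery wherever CNC or AzBio +10 is not part of the clinic's routine work-up.
- Allow consent after surgery only when both pre-operative results are on file.
- Count the 90-day window back from surgery instead of from consent.

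In the same amendment, reconcile inclusion criterion 5 (section 4.3.1 and the synopsis) with consent before surgery, and settle on one definition of enrolment across sections 5.1 and 5.4.2.

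The cost is amendment wording, plus the loss of a few candidates who come forward after surgery without a baseline and would become ineligible. Counting from surgery works the other way: it keeps valid pre-operative results that the present window rejects only because consent came later.

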12.5 Confidentiality

A Case Report Form (CRF) will be completed for each study subject, summarizing all clinical and study data. The CRF contains confidential material. Subjects will only be referred to in the CRF by their subject numbers in order to retain subject confidentiality. Specific instructions to complete the CRF shall be provided to the clinical investigation team as appropriate.

The CRFs are to be retained by the Investigator for a period of time as determined by local regulations.

12.6 Protocol Deviations and Amendments

The Investigator must receive prior approval from the Sponsor, and the IRB when necessary, to deviate from the protocol except in cases of emergency to protect the rights, safety, and well-being of the subjects. Emergency protocol deviations must be documented and reported to the Sponsor and the IRB.

No changes in the protocol or informed consent shall be effected without mutual agreement between the IRB and the Sponsor. Changes related to the scientific

intent of the study shall be documented in the protocol amendment and requires signatures from both the sponsor and the participating investigator.

12.7 Data Management

Data collection is performed using Case Report Forms (CRFs) and paper test outcome measures. Data will be stored in an electronic data capture system (EDC) maintained by the Sponsor. Site personnel will be trained on the completion of the CRFs.

12.8 Record Keeping and Retention

All source documents, CRFs, and trial documentation will be kept by the Investigator(s) for the appropriate retention period as stipulated by local regulations and ICH-GCP.

4.0	Modification to Group A schedule	[name]	12/13/2018
5.0	Corrections to study language	[name]	12/18/2018
6.0	Modification to Group A and B schedule	[name]	12/21/2018
6.1	Clarification to sites for expectation for study monitoring and data collection	[name]	1/31/2019
6.2	Update protocol to include Recipient Services video call pilot information and materials, clarification/modification of Group A protocol	[name]	4/11/2019
